Appendix D: Detailed survey methodology & sample size estimation

Deviations from general statistical approach in this protocol

The sample size details below follow the general statistical approach for SCI coverage surveys. For this survey the enumerators will interview all eligible SAC per household to try and gather more information regarding those SAC who do not attend school. It is not anticipated that this will impact the minimum number of interviews per village.

Sample size details

Values imputed to the sample size calculation were:

- # children in each implementation unit = 391
- Number of children interviewed in each household on average = 2
- Number of individuals targeted in each village = 24
- Non-response rate = 20%
- Margin of error for confidence interval = 9%
- Expected true coverage = 50%
- Intra-class correlation coefficient = 0.1
- Confidence level of intervals = 95%

Statistical approach to coverage survey

Statistical approach to coverage survey methodology & sample size estimation

Scope

These principles are applicable for assessing treatment coverage in all MDA settings where the method of sampling is two stage cluster sampling.

Implementation units monitored

Logistical and financial constraints will almost always mean that not all implementation units will be assessed. There are two main options when choosing which implementation units to assess:

- 1. Non-random selection of implementation units where units are chosen for their particular properties. These properties may be due to reported coverage rates or other external factors (e.g. donor-support; geography). Where the implementation units are chosen for their reported coverage rates a mix of districts that have reported low and high coverage are often chosen. This is to allow comparison between districts and to investigate if particularly low performing district may actually have performed better than expected perhaps due to the population being lower than estimated. Non-random selection is most commonly used in programs covering large areas (such as large countries) where logistical and cost constraints mean only a small number of implementation units can be visited. However, this method does not enable an estimate of coverage at the population level to be obtained.
- 2. Random selection of implementation units where the units are chosen randomly from a list of all implementation units, with or without weighting for population size. This strategy allows estimation of coverage at a program level if sufficient implementation units are visited. This strategy is most commonly used in programs that cover relatively small areas where travel distances between implementation units is not prohibitive.

Sample size calculation

The sample size calculations find the number of primary sampling units (PSUs; normally villages) required in order to have expected 95% confidence intervals of \pm 9% when true population coverage is 50%, given a specified target number of households (HHs) to survey in each PSU. It is assumed that coverage estimates of a pre-specified precision are required at an IU-level (the highest level of resolution) and that sample size calculations need not aim to achieve a pre-specified precision for any particular sub-group (e.g. attending vs. non-attending children). Thus the precision of coverage estimates for sub-groups will vary according to their frequency in the survey.

The parameters used in the calculation are:

- **True implementation unit coverage assumed = 50%**. This is chosen as it is the most conservative level and will give the largest sample size required of any assumed coverage percentage.
- Number of HHs sampled in each primary sampling unit = variable. This is chosen by the program management and is primarily motivated by logistical issues such as team size and expected distances between PSUs. Arguably the biggest driver of cost in coverage surveys is the staff costs (per diems) for enumerators. Therefore we try to minimise the time needed for a survey (person-hours), given a pre-specified precision. A cluster size (number of HHs per village) that permits two villages to be surveyed per day rather than just one, is preferable, and will minimise the time needed for the survey. We assume the maximum number of villages that can be surveyed per day is 2, if a relatively small number of HHs are interviewed per village.
- Number of individuals in the implementation unit: The average IU population size is considered. Often this will make little difference to the estimated sample size required, though may do when IUs are small. (see below for further options when implementation units are small).
- Differences between PSUs in coverage: Intra-class correlation coefficient = 0.1. An intra-class correlation coefficient (*rho*) of 0.1 is assumed. This is based on a review of coverage survey data from several countries: Baker et al. (Baker, et al., 2013), suggested a design effect of approximately 6 is appropriate when designing a district-level NTD PCT coverage survey based on coverage survey results from several countries in sub-Saharan Africa. Assuming approximately 50 individuals were surveyed per district in the reviewed surveys (though this is not explicitly reported in the paper), leads to an estimate of *rho* around 0.1. In countries where IUs are smaller than a district and implementation may therefore be expected to be more homogeneous within an IU, a smaller value of *rho*/design effect may be more realistically assumed during sample size calculations.
- Margin of error for confidence intervals. A maximum margin of error of 9 percentage points on a 95% confidence interval for the IU coverage estimate is specified.
- Width of confidence intervals calculated during the analysis = 95%. This is a standard metric.
- Number of adults and children to sample in each HH = 2. This is generally assumed to be two as only two SAC, or two SAC and two adults, per HH should be interviewed, with the individuals being randomly selected.
- Expected non-response rate = 20%. The expected non-response rate is assumed to be 20% when adults are being surveyed to allow for less than two adults on average in a HHs. When only SAC are being surveyed, this may be lowered to 12%.

Sample size calculations when implementation units are small

When implementation units are small (e.g. health care centres), and comparable to PSU sizes in some larger surveys, then the sampling methodology may be altered. In this instance, we would assume the overall program to be the implementation unit and the implementation unit to be the primary sampling unit. The sample size calculation would then proceed as normal but would instead calculate the number of implementation units required to have expected 95% confidence intervals of ±9% when true population coverage is 50%, given a specified number of HHs to survey in each implementation unit. This methodology will generally require HH lists to be available for random HH selection. Unbiased estimates of population

coverage will then be calculable, assuming that the implementation units to be surveyed were randomly selected and a sufficient number (>15) were surveyed.

Selection of primary sampling units

Selection of primary sampling units is conducted by an SCI biostatistician. There are two main options when selecting PSUs to survey:

- 1. PSUs are selected from a list of all PSUs within the implementation unit, with no reference to population size. In this instance, every PSU has an equal probability of being selected and consequently HHs in small PSUs are more likely to be selected than HHs in large PSUs due the same number of individuals being interviewed in each PSU. This selection method is most commonly used when population sizes of the primary sampling units are not known. Analyses of coverage rates and associated 95% confidence intervals are be performed with and without adjustment for PSU size, collected as part of the survey.
- 2. PSUs are selected from a list of all PSUs within the implementation unit, with probability proportional to population size. In this instance, larger PSU's have a higher probability of being selected that smaller PSUs, leading to an equal probability of each individual in the implementation unit being selected. Analysis therefore does not require any adjustment for population size. Selection is performed without replacement to guard against the possibility of especially large PSUs being selected multiple times.

Sampling of individuals within a HH

Our standard protocol is for two SAC and two adults (if eligible for treatment) to be interviewed in each HH. Much of the differences in whether or not people received treatment is often between HHs rather than between individuals within a HH. If we were to interview everybody in the same HH then if particularly large HHs were surveyed the interview process could take a very long time meaning either that the teams would have to stay in the villages longer, or reduce the number of houses visited within some villages, neither of which is optimal. We believe that this method will not induce any biases as long as the protocol is followed of randomly selecting from the list of all eligible individuals in the HH.

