Figure 2: Results from previous coverage survey in 2014. Chikwawa, Rumphi and Salima were selected to be revisited during the 2016 coverage survey.

2016

The 2016 coverage survey was conducted in six districts. One district in each region was purposively selected (Chikwawa, Rumphi and Salima), as these were previously surveyed during the 2014 coverage survey and results had demonstrated a need for improvement. In addition, three other districts randomly selected, one from each of the same three region were also surveyed Mchinji, Karonga and Neno districts.

Overall, the surveyed coverage was above the WHO recommended coverage of 75% of SAC in 5 of 6 districts surveyed. When adjusting for population size Mchinji fell below the 75% coverage for SAC. Reported coverage was not significantly different from surveyed coverage in four of the districts for ALB and PZQ, reported coverage was significantly different than surveyed coverage in the remaining two remaining districts, one higher and one lower than reported.

This survey also found there was a significant difference in the coverage between those who do and do not attend school for all districts and there was no significant difference in coverage between the genders. The full protocol and recommendations report can be found here:

https://share.imperial.ac.uk/fom/IDE/SCI/The%20Hub/MWI_2016CoverageSurveyProtocol_EN.docx

https://share.imperial.ac.uk/fom/IDE/SCI/The%20Hub/MWI_Coverage_Recommendations_Report_ EN.docx

Details of the MDA in Malawi 2017

The MDA took place between the 10-14th July 2017. The MDA was conducted in every district in Malawi except the islands of Likoma. SAC were targeted in every district and treatment predominantly delivered in schools for the SAC, as well community-based treatments for children who do not attend school and adults in the high-risk areas.

In addition to the standard radio campaigns and social mobilisation that are conducted annually, the MoH was supported by SCI and Development Media International (DMI) with the delivery of an enhanced media plan which involved 3×1 minute radio clips which started with the Doctor testimonial (25/6/17 - 1/7/17), followed by the Mother testimonial (2/7/17 - 8/7/17) and lastly the clip "Give me my breakfast" Appendix F. Each of the clips was broadcast 70 times (7 times adjacent to the News), across 9 radio stations and in 4 languages: Chichewa, Lhomwe, Tumbuka and Yao.

Coverage targets for MDA in 2017

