Survey Objective (SO) 1. To measure validated treatment coverage of PZQ and ALB in SAC, and adults relative to coverage targets

SO 2. To compare reported and validated coverage of PZQ and ALB for SAC and adults

SO 3. To assess coverage in SAC and adults disaggregated by gender

SO 4. To assess coverage in SAC disaggregated by school attendance

SO 5. Collect information on why targeted eligible individuals did not receive or accept treatment

- SO 6. To assess the impact of radio campaigns on improving knowledge about schistosomiasis
- SO 7. To assess whether radio campaigns improved attendance/coverage of treatment with PZQ and ALB

Where validated coverage rate is defined as:

Total number of interviewed individuals that ingested the target drug Total number of interviewed individuals * 100 %

Note that people interviewed but with missing information on whether they ingested the drug will be assumed to have **not** taken the drug for the purposes of calculating validated coverage.

Study Design

Overview

The coverage survey will take place in nine implementation units (IUs) known as the district. Each IU will be considered separately. Within each IU, the survey will be household (HH) based in randomly selected villages. See Appendix D for a detailed explanation of the statistical approach to the coverage survey.

Survey team

Interviewers must not have been involved in any previous activities related to the NTD programme, specifically the MDA, to ensure that they remain unbiased.

Selection of enumerators will be done by the Programme Managers, ensuring that none of the interviewers were involved with the MDA in July 2017. The majority of interviewers have experience in coverage surveys, but everyone will attend compulsory training to ensure standardisation of knowledge and ability to carry out coverage surveys. Training will include teaching about schistosomiasis and soil transmitted helminth infections as well as familiarisation with the health questionnaires and the phones that the information will be stored on.

Although programme managers will not take part in any of the individual interviews in interviewee households, they will facilitate in the training and logistics of the survey as well as support the teams of enumerators if problems arise.

See Appendix A for more details of the survey teams and logistics.

Timing of survey

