Mchinji	Surveyed Previously	
Rumphi	Surveyed Previously	
Ntcheu	Not surveyed previously	
Dedza	Not surveyed previously	Yes
Chitipa	Not surveyed previously	

Number of villages and households to survey within each IU

Sample size calculations indicated that 17 villages per IU, and 15 HHs per village are required to obtain 9% precision on the coverage of SAC and adults within each district. As the MDA was community-wide, two adults will be randomly sampled, and to capture more information about school attendance rates, all eligible children within a HH will be interviewed. See Appendix D for full details of sample size calculations.

Selection of villages to survey within each IU

A list of all traditional areas (TAs), and all their villages, within the selected districts were collected from the district health offices. The list of all TAs and their villages will ensure all villages have the opportunity to be selected. Each village was allocated a number and was then randomly selected by the in-country team using a random number generator until 18 villages per district were selected. The sample size calculation requires 17 villages, for logistical purposes 18 villages have been selected so that each team will visit 6 villages per district.

A short list of 'reserve villages' was provided, such that if a selected village cannot be visited for security or other unpredictable reasons, it can be replaced with another in the same district. See Appendix B: Coverage Survey Interviewer Manual for more details. Appendix E has a list of all selected villages and reserves

Selection of households to survey within each village

HH selection will be performed on site. Selection will be random, with the methodology dependent on whether HHs lists are available (see data collection protocol). If lists are not available HH selection will by the modified random walk procedure (please see data collection protocol).

Although ideally the survey would include nomadic populations and transient communities, because this is a HH-based survey, those without a fixed residence at the site selected for the coverage survey will not be included in the survey target population.

Selection of individuals to survey within each household

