APPENDIX B: Malawi 2017 Coverage survey interviewer manual

Before arriving at the village

- The team leader should ensure that the village leader is notified of the study at least one week before the survey. The district coordinator may be able to help with this.
- The village leader should be asked if they can provide a list of all households in the village when the team arrives

Arriving at the village

- It is important to be at the village when people are available. This means interviewers should be in the village and ready to start at 8am every day.
- The first thing the team should do when arriving at the village is to seek out the head of the village:
 - 1. Introduce the team and ask for permission to survey
 - 2. Ask the head of the village for a list of houses in the village
 - 3. If a list of houses is available, select households using the 'village list' method
 - 4. If a list of households is not available, select households using the 'modified random walk' method
- The team leader will be responsible for completing the village questionnaire by interviewing the village leader:
 - The **GPS co-ordinates** of the village should be entered on **arrival and departure** if the data is being collected on paper forms

What to do if a village cannot be visited

If a selected village cannot be visited for security or other unpredictable reasons, replaced the village with the first reserve village in the same district that hasn't yet been visited.

Selected villages should only be replaced with those on the reserve list in extreme circumstances where it is impossible to survey that village, and not for reasons of distance, access difficulty and so on. It is important to document in the field report any villages that have been replaced and the reason for this replacement, as this could be a reason for biased coverage results.

Selecting households to interview

20 households will be randomly selected per village.

Definition of a household

We define a HH to be "a group of persons who normally live and eat their meals together in the household, and did so during the time of the survey". These people may or may not be related by blood, but make common provision for food or essentials for living and they have only one person whom they all regard as head of the household"

If the HH comprises of one man with more than one wife then all wives and any children should classified as one HH.

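### Villages are drawn with equal probability and a fixed household take, but validated coverage is defined without weights, and neither the size-adjusted nor the unadjusted estimate is named as the one that counts

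*Protocol*

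**What the plan says.** **Selection of villages.** The protocol's section on selecting villages within each IU says: "Each village was allocated a number and was then randomly selected by the in-country team using a random number generator". No size measure enters, so this is option 1 of Appendix D (Selection of primary sampling units), although the protocol does not label it so.

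**Household take.** The take is fixed. The main text says "Sample size calculations indicated that 17 villages per IU, and 15 HHs per village are required to obtain 9% precision", and Appendix B says "20 households will be randomly selected per village". The two numbers disagree, but either is the same for every village.

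**Stated consequence.** Appendix D says of option 1 that "every PSU has an equal probability of being selected and consequently HHs in small PSUs are more likely to be selected than HHs in large" ones. It adds that sampling proportional to size would need no size adjustment in the analysis.

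**Definition of the outcome.** Study Objectives defines validated coverage as a ratio, printed as "Total number of interviewed individuals that ingested the target drug Total number of interviewed individuals", with no weight. Data collection and analysis mentions clustering but not weighting.

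**Planned analyses.** Appendix D, option 1: "Analyses of coverage rates and associated 95% confidence intervals are be performed with and without adjustment for PSU size". It does not rank the two.

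**Past experience.** Previous Coverage Surveys, 2016: "When adjusting for population size Mchinji fell below the 75% coverage for SAC". Mchinji is again on the district list.

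**The concern.** SO1 and SO2 are about the district. Reported coverage is persons treated over persons registered across the whole district. For Mchinji, school praziquantel, it is 135,519 / 157,984 = 86%. An unweighted survey proportion under this design instead estimates coverage tilted towards small villages. If coverage differs by village size, a gap between surveyed and reported coverage could come from the sampling and not from misreporting. The comparison with 75% has the same problem.

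The protocol's only written definition of the outcome is the version that its own appendix describes as tilted. With two drugs and two groups (SAC and adults), each district has four pairs of estimates, and no rule says which member of a pair is used. A district near 75% could be reported as above or below the target depending on a choice made after the data are seen.

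**Working it through.** **1. The protocol's own figure.** Inputs from Appendix D, Sample size details: coverage 50%, margin 9 points, 95% confidence, intra-class correlation 0.1, 24 individuals per village, 2 per household, 20% non-response. The 15 households come from the main text.

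- Simple random sample: 1.96² × 0.25 / 0.09² = 118.6
- Design effect: 1 + (24 − 1) × 0.1 = 3.3
- Children per IU: 118.6 × 3.3 = 391 (stated: 391)
- Per village: 15 × 2 × 0.8 = 24
- Villages: 391 / 24 = 16.3, rounded up to 17 (stated: 17; 18 are drawn for logistics)

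The plan's calculation reproduces. The factor 3.3 covers clustering only and has no term for unequal weights.

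**2. Margin of a size-weighted estimate.** Size weights are constant within a village, so they multiply the variance of the average of the village means by 1 + CV², where CV is the coefficient of variation of village size:

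margin = 1.96 × √[ p(1 − p) × 3.3 × (1 + CV²) / (24 × villages) ]

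The CV is not in the protocol. The values below are assumptions, and size is taken as unrelated to the variability of coverage.

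| Assumed CV | Design effect | Margin at 50%, 18 villages | Margin at 75%, 18 villages | Villages for ±9 at 50% |
|---|---|---|---|---|
| 0 (unweighted) | 3.30 | ±8.6 | ±7.4 | 17 |
| 0.3 | 3.60 | ±8.9 | ±7.7 | 18 |
| 0.5 | 4.13 | ±9.6 | ±8.3 | 21 |
| 0.75 | 5.16 | ±10.7 | ±9.3 | 26 |
| 1.0 | 6.60 | ±12.1 | ±10.5 | 33 |

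At 75% coverage the unrounded unweighted margin is 7.42. It reaches 9 points when 1 + CV² = (9 / 7.42)² = 1.47, that is, at a CV of about 0.69.

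**3. Can the choice move a district across 75%?** An illustration with assumed figures: half the sampled villages are small with 80% coverage, and half are three times larger with 72%.

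- Unweighted: (80 + 72) / 2 = 76.0%
- Size-weighted: (1 × 80 + 3 × 72) / 4 = 74.0%

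This shows the mechanism only. Neither village sizes nor coverage by village size is given, so the actual bias cannot be calculated.

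**4. What a design weight needs.** All SAC in a selected household are interviewed, so village households / households completed serves for SAC. Only two adults are drawn per household whatever its size, so adults in large households stay under-represented unless a within-household factor is added. The Village Questionnaire asks for the number of households (item 10), and the Household Questionnaire counts adult men and women (items 11 and 12).

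**The case against.** The strongest reply is that adjustment is already planned. Appendix D discloses the tilt and promises both analyses, and the forms collect village size. The formula in Study Objectives may be meant only to fix numerator and denominator, including the rule that missing answers count as not ingested, and not to exclude weights. Which estimate leads could be settled in a separate analysis plan. This is also descriptive monitoring, with no formal pass/fail rule.

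Much of this stands. A reader might infer that weighting is absent from the plan; it is not. A reader might also infer that the protocol names the unweighted figure as the headline; it does not rank the two. What remains is something the protocol states, not something it leaves out: its one written definition is unweighted, and the two analyses have no order.

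The 2016 episode also invites a stronger reading, that adjustment is known to have overturned a clear result. The text gives no estimates or intervals for Mchinji, and it is unclear whether Mchinji was the sixth of the six districts or a further one falling short. If it was the sixth, the statement that five of six exceeded 75% may already be the adjusted result. The wording supports only that Mchinji's point estimate crossed 75% on adjustment.

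The weights are also imperfect. In random-walk villages, households come only from those along one direction, and the village household count may be the respondent's guess. That is a good reason to show both results, but not to leave the main one unnamed.

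**Conclusion.** The point holds and should be fixed, as an inconsistency between the outcome definition and the sampling design. Followed literally, the definition gives SO1 and SO2 a figure that Appendix D itself describes as tilted to small villages, and the plan offers a second figure without saying which one is compared with 75% or with reported coverage.

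The direction and size of the bias are unknown. A reader might infer that the ±9-point precision is lost. That is conditional on a village-size CV that the protocol does not give. At the plan's own 50% coverage with 18 villages, a CV of 0.3 still gives ±8.9, while 0.5 to 1.0 gives ±9.6 to ±12.1. Near 75%, where the target comparison is made, the margin stays within 9 points up to a CV of about 0.69. All these figures assume 24 interviews per village and an intra-class correlation of 0.1, and they cover village-size weights only. The within-household factor for adults would add to the variation in weights.

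**What to change.** - **Definition (Study Objectives).** Define validated coverage as a design-weighted ratio, make it the primary estimate for SO1 and SO2, and bring Appendix D into line. Use villages as primary sampling units in the variance. Keep the unweighted proportion as a sensitivity analysis.
- **Weights for SAC.** Village households / households completed.
- **Weights for adults.** The same, multiplied by adults resident / adults interviewed in the household.
- **Caveats to state.** Weights are approximate in random-walk villages and where the household count is the respondent's estimate. The section on implementation unit selection says traditional areas were randomised as well as villages; if that was a separate stage, its selection probability belongs in the weight.
- **Precision.** State that ±9 points makes no allowance for unequal weights, and give the weighted margin as a conditional range, ideally with village-size CVs from the 2014 and 2016 surveys if those data are available.

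**Cost.** No new fieldwork or form items are needed, since household and adult counts are already collected. The cost is revised wording, some work to build and check the weights, and a stated margin that may be less favourable.
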